Quantification of Pain Relief with Gonadal Vein Embolization for Pelvic Congestion Syndrome

December 6, 2018

Investigators

[name] MD (Trainee), [name] MD (PI/Mentor), [name] MD (Mentor), [name] MPH (Research Manager). Department of Radiology.

Purpose of Project

To quantify the degree of pain relief following gonadal vein embolization.

Background

Chronic pelvic pain, defined as lower abdominal or pelvic pain lasting for greater than 3-6 months, affects almost 40% of women during their lifetime.^{1,2} Pelvic congestion syndrome (PCS) accounts for up to 30% of those with chronic pelvic pain, and is characterized by pelvic pain, dyspareunia, dysuria, and dysmenorrhea.^{1,2} The most common underlying cause of PCS is incompetence or obstruction of the gonadal veins, resulting in painful congestion of the pelvic and perineal venous vasculature.^{2,3}

Medical treatment is first line, and aims to suppress ovarian function and induce vasoconstriction of the venous system.^{1,2} The most common medications used are medroxyprogesterone acetate (MPA) or the GnRH analogue goserelin, although this often necessitates estrogen replacement therapy to counteract the symptoms of ovarian suppression.¹ Unfortunately, efficacy and long-term pain relief from medical therapy is limited.²

Invasive options include total abdominal hysterectomy and bilateral salpingo-oophorectomy (TAH-BSO), extraperitoneal gonadal vein resection, and laparoscopic gonadal vein ligation.^{1,2} Efficacy of TAH-BSO is poor, with 33% of patients reporting residual pain, and 20% reporting recurrent pain.¹ Gonadal vein resection and ligation have shown positive results, although are more invasive, and result in longer hospital stays, and have higher complication rates.²

Since its development in the early nineties, gonadal vein embolization has become the treatment of choice.^{1,2} A number of studies have reported pain relief ranging between 47 to 94% of patients, that has been maintained through up to 36 months of follow up.² Complications are rare, and include gonadal vein perforation, coil migration, and recurrent varices.^{1,2} The procedure involves obtaining venous access, performing venography of the gonadal veins, and subsequently embolizing one or both gonadal veins. Multiple embolic agents have been demonstrated in the literature, including liquid sclerosants (such as sodium tetradecyl sulfate, polidocanol), glue (such as n-butyl cyanoacrylate), Amplatzer plugs, and coils.¹⁻⁴

Coil embolization of the gonadal veins has been shown to decrease pain in those affected by PCS, although the degree of relief has not yet been quantified.⁵⁻⁷ This study's primary aim is to quantify the degree of pain relief with gonadal vein embolization. A patient questionnaire, called the Pelvic Congestion Symptom Score (PCSS) has been developed specifically for this project.

The PCSS is a 4-question tool used for evaluation of PCS symptoms both before and after gonadal vein embolization. It encompasses symptom frequency, severity, impact on activities, as well as happiness and quality of life, with scores ranging from 0 (asymptomatic) to 16 (disabled). Data gathered from the PCSS will help identify the degree of relief from PCS symptoms, as well as identify patients who are treatment resistant. Patients with no response or incomplete response to therapy will be further studied to identify predictors of ineffective treatment, possibly identifying patients who would benefit from more aggressive treatment.

Methods

This prospective study will enroll a maximum of 30 patients 18 years of age and older who are candidates for gonadal vein embolization in the Interventional Radiology division at the University of Kansas Medical Center from October 1, 2018 to October 1, 2019. Following clinical evaluation, the patients will fill out the PCSS survey prior to their procedure. Patients will then fill out the same PCSS survey at 4 weeks, 90 days, 180 days, and 360 days following their procedure. Follow up surveys will either be performed by phone or at a relevant follow up appointment. Relevant clinical information will be obtained from patients' medical records and the Picture Archiving and Communication System (PACS), including demographics, clinical history, imaging findings, and intervention details. Secondary analysis will be performed to determine whether there are clinical or imaging factors that are predictive of a positive response to treatment, or poor response to treatment.

Specific Objectives

- **Null Hypothesis:** There is no significant difference in chronic pelvic pain following gonadal vein embolization, and/or the PCSS is an invalid tool for grading symptomatic improvement following gonadal vein embolization.
- **Primary Objective:** To quantify the degree of pain relief in patients undergoing gonadal vein embolization with coils.
- **Secondary Objective:** To identify clinical or imaging factors that are predictive of a positive response to treatment, or poor response to treatment.

Inclusion Criteria

- Female patients 18 years of age or older
- Meet the clinical and imaging criteria for the diagnosis of PCS and have no contraindications to coil embolization of the gonadal veins.
- Patients who are treated with coil embolization of the gonadal veins in the Interventional Radiology division between October 1, 2018 to October 1, 2019.

Exclusion Criteria

- Patients less than 18 years of age.
- Patients who are found to have an underlying cause of pelvic congestion syndrome unrelated to venous congestion and insufficiency. This includes, but is not limited to, nutcracker syndrome, or a mass resulting in extrinsic compression of the gonadal veins.
- Patients who have received prior surgical therapy for PCS, including bilateral salpingo-oophorectomy (TAH-BSO), gonadal vein resection, or gonadal vein ligation.

Risks

As the primary objective of this study is to quantify improvement in patient pain following gonadal vein embolization via the use of the PCSS questionnaire, there are no expected risks to be incurred by patients participating in this study.

Statistical Analysis

Descriptive statistics, correlations, and multivariate linear and/or logistic regression models will be utilized to analyze the data by trained professionals in the Radiology and/or Biostatistics Departments at KUMC.

Data Management

Data collection forms will be created and managed in REDCap. Patient information will be kept in password-protected databases and will be deidentified for analyses and presentations of results. All study documents will be stored on limited access KUMC protected network drives and any paper copies of source documents will be locked in the Radiology Research Office.

References

1. Ignacio EA, et al. Pelvic Congestion Syndrome: Diagnosis and Treatment. *Semin Intervent Radiol* 2008; 25(4):361–368.
4. Lopez AJ. Female Pelvic Vein Embolization: Indications, Techniques, and Outcomes. *Cardiovasc Intervent Radiol* 2015; 38(4):806–820.

Table Outlines

Table 1: Patient Characteristics

- Demographics
 - Age (mean, SD)
 - Race (n, %): White, Black or African American, Asian, American Indian or Alaska Native, Native Hawaiian or Other Pacific Islander, Other / Unspecified
 - Ethnicity (n, %): Hispanic, Non-Hispanic
 - Height (mean, SD)
 - Weight (mean, SD)
 - Parity (mean, SD)
- Symptoms
 - Dyspareunia (mean, SD)
 - Dysuria (mean, SD)
 - Dysmenorrhea (mean, SD)
- Presence of Varicosities
 - Unilateral Gluteal (mean, SD)
 - Bilateral Gluteal (mean, SD)
 - Unilateral Vulvar (mean, SD)
 - Bilateral Vulvar (mean, SD)
 - Unilateral Perineal (mean, SD)
 - Bilateral Perineal (mean, SD)
 - Unilateral Upper-Inner Thigh (mean, SD)
 - Bilateral Upper-Inner Thigh (mean, SD)

Table 2: Imaging and Intervention Characteristics

- Right Gonadal Vein Diameter (mm, SD)
- Left Gonadal Vein Diameter (mm, SD)
- Right Internal Iliac Vein Diameter (mm, SD)
- Left Internal Iliac Vein Diameter (mm, SD)
- Side of Intervention (n, %): Left, Right, Bilateral
- Number of Coils Used Per Side (n, %)

Table 3: Pain Scores

- Pre-Intervention
 - Number of Days a Week Pelvic Pain is Experienced (mean, SD)
 - Severity of Pelvic Pain (mean, SD)
 - Limitation from Pelvic Pain (mean, SD)
 - Effect on Happiness and/or Quality of Life (mean, SD)
 - Total Score (mean, SD)
- 4 Weeks Post-Intervention
 - Number of Days a Week Pelvic Pain is Experienced (mean, SD)
 - Severity of Pelvic Pain (mean, SD)
 - Limitation from Pelvic Pain (mean, SD)
 - Effect on Happiness and/or Quality of Life (mean, SD)
 - Total Score (mean, SD)
- 90 Days Post-Intervention
 - Number of Days a Week Pelvic Pain is Experienced (mean, SD)
 - Severity of Pelvic Pain (mean, SD)
 - Limitation from Pelvic Pain (mean, SD)

- Effect on Happiness and/or Quality of Life (mean, SD)
 - Total Score (mean, SD)
- 180 Days Post-Intervention
 - Number of Days a Week Pelvic Pain is Experienced (mean, SD)
 - Severity of Pelvic Pain (mean, SD)
 - Limitation from Pelvic Pain (mean, SD)
 - Effect on Happiness and/or Quality of Life (mean, SD)
 - Total Score (mean, SD)
- 360 Days Post-Intervention
 - Number of Days a Week Pelvic Pain is Experienced (mean, SD)
 - Severity of Pelvic Pain (mean, SD)
 - Limitation from Pelvic Pain (mean, SD)
 - Effect on Happiness and/or Quality of Life (mean, SD)
 - Total Score (mean, SD)

Table 4: Primary Outcomes

- Mean Reduction of Pain Score 4 Weeks Post-Procedure (Mean, SD)
- Mean Reduction of Pain Score 90 Days Post-Procedure (Mean, SD)
- Mean Reduction of Pain Score 180 Days Post-Procedure (Mean, SD)
- Mean Reduction of Pain Score 360 Post-Procedure (Mean, SD)

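### The only stated null hypothesis joins no change in pain to invalidity of the PCSS with and/or, and the planned data cannot by themselves refute the second part

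*Protocol*

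**What the plan says.** The Specific Objectives section of the Protocol gives a single null hypothesis, which reads: "There is no significant difference in chronic pelvic pain following gonadal vein embolization, and/or the PCSS is an invalid tool for grading symptomatic improvement". The primary objective beside it is to quantify pain relief after coil embolization, and the secondary objective is to find predictors of good or poor response. Neither mentions validating the questionnaire.

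On the instrument, the Background says: "A patient questionnaire, called the Pelvic Congestion Symptom Score (PCSS) has been developed specifically for this project". On its content: "It encompasses symptom frequency, severity, impact on activities, as well as happiness and quality of life". The total runs from 0 to 16.

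The PCSS is completed before the procedure, and on follow-up the Methods say: "Patients will then fill out the same PCSS survey at 4 weeks, 90 days, 180 days, and 360 days following their procedure". The Inclusion Criteria admit only women treated with coils, so there is no untreated group. In the Table Outlines, Table 3 repeats the four PCSS items and the total at each time, and Table 4 lists mean score reductions. Dyspareunia, dysuria and dysmenorrhea appear only in Table 1, as patient characteristics, with no follow-up rows.

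The Background also takes a treatment effect as known: "Coil embolization of the gonadal veins has been shown to decrease pain in those affected by PCS".

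**The concern.** A null hypothesis fixes what its rejection would assert. This one contains two claims of different kinds, one about the procedure and one about the measuring tool, and and/or does not say how they combine. The same data would have to settle both, although the change in pain is read from the tool whose validity is in question.

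What is at stake is the conclusion. An author who sees a clear fall in PCSS and declares the null rejected could report, on the protocol's own wording, that the PCSS has been shown valid. If the score does not fall, an ineffective procedure and an insensitive tool are hard to tell apart, and retaining the null says nothing definite about either.

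**Working it through.** **Inputs.** The null wording and the eligibility criteria come from the Protocol's Specific Objectives and criteria lists, the schedule from Methods, the status of the PCSS from Background, and the reported outcomes from Tables 1, 3 and 4. The Protocol gives no alpha, effect size or standard deviation, and no derivation of the maximum of 30, so there is no figure of its own to reproduce.

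**Step 1: what rejection asserts.** Let A = no change in pain and B = the PCSS is invalid.

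- not (A or B) = (not A) and (not B): pain changed and the tool is valid.
- not (A and B) = (not A) or (not B): pain changed, or the tool is valid, or both.

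| Pain | PCSS | Null as A or B | Null as A and B |
|---|---|---|---|
| unchanged | invalid | true | true |
| unchanged | valid | true | false |
| changed | invalid | true | false |
| changed | valid | false | false |

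The or null is true in 3 of 4 states and the and null in 1 of 4. They differ in 3 − 1 = 2 states, those where exactly one part is true. In the second row the and null is false although pain has not changed, so rejecting it need not mean pain relief.

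**Step 2: can the data refute B?** To refute B, something other than the PCSS has to show that the score moves with real improvement. The documents name no other symptom measure at follow-up, no untreated group and no repeated baseline. The Table 1 symptoms are recorded once. The PCSS change is therefore the only named evidence of symptom change, and it has to serve for both parts.

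**Step 3: illustration.** Suppose pain does not change but mean PCSS falls by d standard deviations of the change score, through expectation, recall or regression to the mean. Assume n = 30 (the stated maximum), a paired t-test and two-sided alpha 0.05. The test and alpha are my assumptions, as are the values of d. Power comes from the noncentral t distribution with 29 degrees of freedom and noncentrality d × √30.

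| d | d × √30 | Probability of a significant PCSS change |
|---|---|---|
| 0.2 | 1.10 | 0.19 |
| 0.3 | 1.64 | 0.36 |
| 0.5 | 2.74 | 0.75 |
| 0.8 | 4.38 | 0.99 |

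A significant fall can thus be likely when the score is not tracking pain. The table does not predict that this will happen here. It shows only that significance of the PCSS change is not a test of B.

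**The case against.** The strongest reply is that, under the inclusive or, a fall in PCSS alone does not reject the null, because B must also be refuted. On that reading the wording sets a stricter bar, and the feared validity claim needs a decision rule that the Protocol does not state. The logic is right, but it does not rescue the text. If a PCSS fall is not enough, the planned data cannot reject the study's only null. If it is treated as enough, validity is asserted without support.

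A second reply is that the clause honestly admits that a null result could reflect the tool. That caution is worth keeping, but as a stated limitation; inside a null hypothesis it becomes a claim that rejection would reverse.

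A third is that coils are already believed to work, so a fall in PCSS shows that the tool responds. This is some evidence, but it is weak and uncontrolled. It also risks circularity: the score is used to show the effect, and the effect to show that the score works.

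A fourth is that the aim is estimation and nothing planned rests on the clause. This stands as a limit on the size of the point.

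Finally, a reader might infer that a validation analysis is missing. The documents do not support that. The Statistical Analysis section lists correlations, and a SAP that is not shown may contain item-level or internal-consistency work. Such work would use the PCSS's own items and would supply no outside reference. Methods also allows clinical information from medical records, but names no symptom measure there that could serve as an anchor.

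**Conclusion.** The point holds as a fault in the stated hypothesis and should be fixed. The null cannot be used as written. Read as or, it is either beyond rejection with the planned data or its rejection claims an unsupported validity; read as and, rejection need not mean pain relief. This rests on the follow-up measures that the Protocol names. It would weaken if an outside symptom measure were in fact being collected at follow-up.

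The effect is confined to the conclusion the trial may draw. No alpha, sample size or Table 4 estimate changes, and the primary objective can be met without this null.

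Two stronger readings are tempting. A reader might infer that the clause causes patients to be mislabelled, because the Background says: "Data gathered from the PCSS will help identify the degree of relief from PCS symptoms, as well as identify patients who are treatment resistant". Those labels would come from the same PCSS scores whatever the null says, so a count of likely non-responders does not measure this fault. A reader might also infer that the null must be tied to one of the four follow-up times, or that the outcome must be renamed because the PCSS covers more than pain. Those are separate matters that the and/or defect does not require anyone to settle.

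**What to change.** Delete the validity clause, so that the null concerns only change from baseline in PCSS score. Suitable wording would be: *PCSS score after embolization does not differ from the score before it.* Add one sentence stating that a fall in PCSS does not by itself establish that the tool is valid; this keeps the caution that the present clause carries. The cost is one sentence reworded and one added, with no new data and no changed analysis.

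Only if validity is to be claimed, make it a separate secondary objective with an external anchor asked at the existing contacts, such as a 0–10 pain rating or a global-change question. This costs one or two extra questions per contact. Patients treated before the change would have no baseline anchor; enrolment opened on October 1, 2018 and the Protocol is dated December 6, 2018, so there may be some. Agreement with such an anchor would show consistency with another self-report, not freedom from expectation effects.

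### Table 4 sets the primary result as four separate visit means, which can mix loss of patients with change in pain if follow-up to 360 days is incomplete and related to response

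*Protocol*

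**What the plan says.** The Table Outlines at the end of the Protocol include Table 4, headed as the primary outcomes. It has four rows, one per follow-up visit. The first is "Mean Reduction of Pain Score 4 Weeks Post-Procedure (Mean, SD", and the rows for 90 and 180 days follow the same pattern. The fourth is "Mean Reduction of Pain Score 360 Post-Procedure (Mean, SD". Each asks for a mean and an SD and nothing else. Table 3 gives the scores themselves in the same format. Rows for categories do ask for a count, for example "Side of Intervention (n, %): Left, Right, Bilateral"; rows for means do not.

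On design, the Methods section states: "This prospective study will enroll a maximum of 30 patients 18 years of age and older". There is one group. On collection it states: "Follow up surveys will either be performed by phone or at a relevant follow up appointment". The Statistical Analysis section names descriptive statistics, correlations, and linear and/or logistic regression. The Background adds: "Patients with no response or incomplete response to therapy will be further studied to identify predictors of ineffective treatment".

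The Protocol gives no expected loss to follow-up.

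**The concern.** A reduction can be computed only for a woman who has a score at the visit. None of the methods named fills in a missing survey or borrows from the same woman's other visits. Applied as listed, they rest each row of Table 4 on whoever answered at that time, and four rows can describe four different sets of women.

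This does no harm if those who stop answering resemble those who continue. It matters if answering depends on relief, and that could go either way: a woman with persistent pain may lose interest in the study, or a woman who feels well may see no reason to reply. In the first case the later rows rise without anyone improving. In the second they fall without anyone relapsing.

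At stake is the reading of the 360-day figure and of how long relief lasts, which four successive rows invite. With a single arm there is no comparison group in which the same loss could be seen or offset. The surveys already scheduled at 4 weeks, 90 and 180 days carry much of the information needed to adjust for such loss, and separate visit means do not use it.

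**Working it through.** The Protocol states no effect size, SD, correlation or loss, so it has no figure to reproduce. From it come the maximum of 30 women, the four follow-up times and the 0 to 16 range of the PCSS. Everything else below is assumed. In each illustration the true mean reduction is the same at every visit, so any drift in the visit means is an artefact.

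**1. Exact example.** Take 18 women with a constant reduction of 8 points and 12 with a constant reduction of 2.
- Everyone observed: (18 × 8 + 12 × 2) / 30 = 168 / 30 = 5.6.
- 10% of the first group and 50% of the second lost by day 360: 16.2 and 6.0 remain on average, and (16.2 × 8 + 6.0 × 2) / 22.2 = 141.6 / 22.2 = 6.38.
- 50% and 10% lost instead: 9.0 and 10.8 remain, and (9.0 × 8 + 10.8 × 2) / 19.8 = 93.6 / 19.8 = 4.73.
- 20% or 40% lost equally from both groups: 5.6, unchanged.

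**2. Simulation with moderate to strong selective loss.** 30 women, true reduction 5, SD 4, correlation 0.7 between visits, 600 replicates per setting. Once lost, a woman stays lost. The log-odds of loss before the next visit is a + b × (last reduction − 5), with a = −2.2 or −2.6 and b = ±0.25 or ±0.5 per point. Between 58 and 75% were still observed at day 360, so 25 to 42% were missing.

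| Who leaves | Observed day-360 mean | Shift from 5 |
|---|---|---|
| Women with less relief (b negative) | 5.65 to 6.57 | +0.65 to +1.57 |
| Women with more relief (b positive) | 4.34 to 3.45 | −0.66 to −1.55 |

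A multivariate-normal likelihood fit to all the reductions in the same data gave 4.96 to 5.04 at day 360.

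The slopes are not mild. Per SD they are 0.25 × 4 = 1 and 0.5 × 4 = 2 on the log-odds scale, which are odds ratios of about 2.7 and 7.4.

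**3. Simulation at the milder slope, over a range of loss.** 30 women, true reduction 6, SD 4, correlation 0.7, log-odds of loss ±1 per SD of the last reduction, 4,000 replicates. Nominal loss is the loss to day 360 if it were unrelated to response. In the selective settings the realised loss is somewhat higher: at 10% nominal, 25.7 women remain, a loss of 1 − 25.7/30 = 14%.

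| Nominal loss | Women left at day 360 (selective loss) | Mean if poorer responders leave | Mean if better responders leave | Mean if loss is unrelated |
|---|---|---|---|---|
| 10% | about 26 | 6.38 | 5.63 | 6.03 |
| 20% | about 22 | 6.69 | 5.29 | 5.99 |
| 30% | about 19 | 6.97 | 5.04 | 6.00 |
| 40% | about 17 | 7.21 | 4.77 | 6.01 |

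The shift is about 0.4 points at the lowest loss and 1.2 at the highest. For scale, the standard error of a mean at SD 4 is 4/√30 = 0.73 with 30 women and 4/√18 = 0.94 with 18.

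**The case against.** The strongest reply is that this is a missing-data question, and the handling of missing surveys, the analysis set and the n per row are commonly left to a statistical analysis plan, which may exist and is not shown. The tables are labelled as outlines, and an outline without an n does not forbid printing one. This stands. The absent n is not a fault in itself, and neither is the absent rule for missing surveys. What remains open to review is the summary that the Protocol does choose for its primary result, together with methods that do not recover a missing score.

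Several stronger readings are tempting, and the Protocol does not support them:
- A reader might infer that the plan prescribes dropping women who stop answering. It never says whether rows use available cases, completers or imputed values; available cases is only what the named methods do by default.
- A reader might infer that the change from 4 weeks to 360 days is confounded. That needs loss, and loss related to response. The Protocol gives no loss figure and defines no test of trend.
- A reader might infer that differences between Table 3 means will disagree with Table 4. That assumes the baseline row keeps every woman, which is not stated.
- A reader might infer that women lost early cannot enter the study of poor responders. No visit is fixed for classing response, so an early score could serve.
- A reader might infer that relieved women are missed because they have no appointment. The surveys can also be done by phone, which weakens that link.

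The size can also be challenged, fairly. Every input is assumed, and the 1.6-point figure comes from the extreme setting. At the milder slope with 10 or 20% nominal loss, the shift of 0.4 or 0.7 is below the standard error of 0.73 for 30 women. The good recovery by a likelihood fit is partly built in, because loss was made to depend only on observed reductions. The fit tested was also not the exact model proposed below. Finally, a repeated-measures model is not the only remedy: restricting all rows to a common set of women is another.

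**Conclusion.** The point holds in conditional form. As outlined, the primary summary is not robust to incomplete follow-up that is related to response: the later means can move with who is still answering, in a direction that cannot be known beforehand. Under the assumptions of the second illustration the day-360 mean moves by about 0.7 to 1.6 points on a 0 to 16 scale; under the third, by about 0.4 to 1.2. With complete follow-up, or loss unrelated to response, there is no bias. The Protocol does not show that such loss will occur, so this is a cheap improvement to a stated choice of summary and not a demonstrated error in the result.

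**What to change.** In Table 4, and in the Statistical Analysis section, make the primary figure at each time the estimated mean reduction with its 95% CI from one repeated-measures model. Visit enters as a factor, baseline PCSS as a covariate, and all collected follow-up scores are used. Keep the observed mean and SD beside it, with the n and the baseline mean of the women contributing at that visit. Printing n alone would show the loss but would not correct for it.

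The cost is wording and a modest amount of analysis; no visits, surveys or patients are added. There are three limits to state. The model assumes that missingness is explained by the scores already observed. With at most 30 women it may need a simple covariance structure. It still leaves out women with no follow-up survey at all, who should be counted and reported separately.
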